 - f. Significant valvular heart disease including moderate or severe mitral or aortic stenosis with an aortic valve area <1.0 cm^2 or mitral valve area <1.5 cm^2), greater than moderate aortic or mitral regurgitation, greater than moderate tricuspid or pulmonic stenosis
11. Restrictive, dilated or hypertrophic cardiomyopathy or constrictive pericarditis
12. Using non-oral prostacyclin when screening;
13. Laboratory parameters during screening:
 - a. Baseline aspartate aminotransferase (AST) or alanine aminotransferase (ALT) ≥ 2 times the upper limit of normal (ULN) or total bilirubin ≥ 1.5 times ULN
 - b. Estimated glomerular filtration rate (eGFR) <60 mL/min by Cockcroft-Gault formula
 - c. Hemoglobin concentration ≤ 100 g/L at screening
14. QTc interval by Fridericia's criteria (QTcF) ≥ 500 msec at screening

15. Malignancy within 5 years before screening visit (with the exception of localized non-metastatic basal cell carcinoma of the skin, non-metastatic carcinoma of the prostate or in-situ carcinoma of the cervix excised with curative results)
16. Alcohol or drug abuse within 1 year before screening
17. A psychiatric, addictive or other disorder that compromises the ability to give informed consent for participating in this study
18. History of organ transplantation
19. Pregnant or nursing females
20. History of HIV
21. Positive hepatitis B surface antigen (HBsAg), hepatitis C antibody (HCV-Ab), or HIV antibody (HIV-ab).
22. Enrolled in another interventional study within 30 days before screening.
23. Any condition that, in the opinion of the investigator, prevents a potential subject from safely participating in the study.

Investigational products, dose, and mode of administration:

Test products: GMA301

Proposed dose levels: 300, 600, and 1000 mg every 4 weeks (Q4W) for 12 weeks

Administration route: IV

Duration of subject participation in the study:

Planned Screening duration: up to 4 weeks.

Planned study duration (Screening to Follow-up): approximately 22 weeks.

Endpoints:

Primary Endpoints

The incidence of Treatment Emergent Adverse Events (TEAE) after the start of GMA301 dosing compared with placebo.

Secondary Endpoints

- Pharmacokinetics
 - Area under the serum concentration- time curve from time zero to the last measurable concentration (AUC_{0-t})
 - Area under the serum concentration- time curve over a dosing interval ($AUC_{0-\tau}$)
 - Observed maximum serum concentration (C_{max})

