4.2. Exclusion Criteria

Subjects who meet any of the following criteria will not be allowed to participate in this study:

1. Diagnosed with WHO Group II, III, IV, V of PH.
2. Using calcium channel blockers when screening.
3. BP $> 160/100$ mmHg at Screening
4. Systolic BP < 90 mmHg at Screening
5. Pulmonary function test: FEV1 $< 60\%$ of predicted, TLC $< 60\%$ of predicted, DLCO $< 60\%$ of predicted
6. One of the following tests with confirmed pulmonary emboli and chronic thromboembolic pulmonary hypertension (CTEPH) following initial diagnosis of PAH:
 - a. Pulmonary ventilation/perfusion scan
 - b. CT pulmonary angiogram
 - c. Contrast dye pulmonary angiogram
7. History of sleep apnea
8. Limited full participation in the 6MWT due to arthritic, neuromuscular,

vascular or other diseases unrelated to PAH

9. History of acute cardiovascular and cerebrovascular events within 6 months before screening.
10. Echocardiogram (ECHO) demonstrating at least 1 of the following:
 - a. LVEF $\leq 50\%$
 - b. Mean end-diastolic left ventricular septal and posterior wall thickness of >12 mm
 - c. Left atrial (LA) area on apical 4 chamber view >20 cm 2
 - d. LA volume by biplane modified Simpsons or area-length methods >55 mL
 - e. LA volume index >29 mL/m 2
 - f. Significant valvular heart disease including moderate or severe mitral or aortic stenosis with an aortic valve area <1.0 cm 2 or mitral valve area <1.5 cm 2), greater than moderate aortic or mitral regurgitation, greater than moderate tricuspid or pulmonic stenosis
11. Restrictive, dilated or hypertrophic cardiomyopathy or constrictive pericarditis
12. Using non-oral prostacyclin when screening;
13. Laboratory parameters during screening:
 - a. Baseline aspartate aminotransferase (AST) or alanine aminotransferase (ALT) ≥ 2 times the upper limit of normal (ULN) or total bilirubin ≥ 1.5 times ULN.
 - b. Estimated glomerular filtration rate (eGFR) <60 mL/min by Cockcroft-Gault formula
 - c. Hemoglobin concentration ≤ 100 g/L at screening
14. QTc interval by Fridericia's criteria (QTcF) ≥ 500 msec at screening
15. Malignancy within 5 years before screening visit (with the exception of localized non-metastatic basal cell carcinoma of the skin, non-metastatic carcinoma of the prostate or in-situ carcinoma of the cervix excised with curative results)
16. Alcohol or drug abuse within 1 year before screening

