17. A psychiatric, addictive or other disorder that compromises the ability to give informed consent for participating in this study
18. History of organ transplantation
19. Pregnant or nursing females
20. History of HIV
21. Positive hepatitis B surface antigen (HBsAg), hepatitis C antibody (HCV-Ab), or HIV antibody (HIV-ab).
22. Enrolled in another interventional study within 30 days before screening.
23. Any condition that, in the opinion of the investigator, prevents a potential subject from safely participating in the study

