7.2.4. Electrocardiogram

7.2.4.1. 12-Lead Electrocardiogram

A resting 12-lead ECG will be recorded after the subject has been supine and be seated or lie for at least 5 minutes at the times indicated in the Schedule of Assessments in [Appendix 6](#).

ECGs will be recorded at screening, Week 4, Week 8, and Week 12.

The 12-lead ECGs will be repeated 3 times, and an average taken of the 3 readings. The QTcF will be averaged and any subject meeting the following criteria will have study medication held and will be followed up:

- QTcF value >500 msec
- QTcF change from the baseline (predose) >60 msec.
- Second- or third-degree heart block or bundle branch block

Additional 12-lead ECGs may be performed at other times if judged to be clinically appropriate or if the data suggests a more detailed assessment of ECGs is required. The investigator (or designee) will perform a clinical assessment of each 12-lead ECG.

Day 1 pre-dose 12-lead ECGs will serve as the baseline assessment. The mean values of PR, QRS, and QTcF will be entered into the eCRF. Averaged values for subsequent ECG intervals should also be entered into the eCRF.

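### The bundle branch block hold in section 7.2.4.1 has no baseline reference, so a stable pre-existing block triggers a hold at each dosing visit without any change on treatment

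*Combined protocol and SAP*

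**What the plan says.** Section 7.2.4.1 sets three ECG criteria and says that "any subject meeting the following criteria will have study medication held and will be followed up". The first is an averaged QTcF above 500 msec. The second is "QTcF change from the baseline (predose) >60 msec". The third is "Second- or third-degree heart block or bundle branch block", with no word tying it to the subject's own earlier ECG.

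On timing, the same section says "ECGs will be recorded at screening, Week 4, Week 8, and Week 12", and also "Day 1 pre-dose 12-lead ECGs will serve as the baseline assessment". The Schedule of Assessments (Appendix 6) marks an ECG at screening, at randomization (Day -1, which may be the day of the first dose) and at Weeks 4, 8 and 12. Injections are at Weeks 0, 4 and 8.

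Section 4.2 has one ECG-based exclusion, number 14: QTcF of 500 msec or more at screening. The synopsis repeats it. Neither list names atrioventricular block or bundle branch block. Exclusion 23 covers any condition that, "in the opinion of the investigator, prevents a potential subject from safely participating in the study".

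The discontinuation list in section 3.6 includes QTcF criteria but no conduction criterion. The section also lets a subject who was not dosed on time return to treatment if the investigator or the Safety Review Committee (SRC) agrees.

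**The concern.** A dose hold on ECG grounds should respond to something that may have happened on treatment. Here it can respond to a trait the subject brought into the study. Bundle branch block may be fixed, so the trigger would recur at each dosing visit with an identical tracing, in active and placebo subjects alike.

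Three things are at stake. The hold itself is unneeded. A review that runs beyond the visit window could delay or lose a dose. Sites may also handle the same unchanged ECG differently: about 10 sites in two countries would be applying a mandatory rule with no stated release condition. A hold triggered in this way also says nothing about the safety of GMA301.

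**Working it through.** The plan states no figure on this point, so the check compares the rules with one another.

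**Step 1. Is each hold trigger protected against a pre-existing finding?**

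| Trigger in 7.2.4.1 | Tied to baseline? | Matching exclusion in 4.2? |
|---|---|---|
| QTcF above 500 msec | No | Yes, number 14 (500 msec or more at screening) |
| QTcF rise above 60 msec | Yes, pre-dose | Not needed |
| Second- or third-degree block, or bundle branch block | No | No |

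Only the third trigger lacks both protections. Exclusion 23 is the nearest cover. It depends on the investigator's view of safe participation, so it may well keep out a subject with higher-degree block, but it need not catch stable bundle branch block.

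**Step 2. At which dosing visits does an unchanged block meet the rule?** There are three doses: Weeks 0, 4 and 8.

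- Literal reading: the ECG at randomization or Day 1 pre-dose counts, as do those at Weeks 4 and 8, so 3 of 3 dosing visits are affected.
- Reading limited to ECGs after the first dose: Weeks 4 and 8, so 2 of 3.
- Reading the clause as covering only events that arise on treatment: 0 of 3. The text does not state this limit for the third bullet, although it does state a baseline comparison for the second.

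**Step 3. What follows from a hold?**

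- It is not a discontinuation criterion in section 3.6.
- It does not by itself count toward the cohort stopping rule, which needs two discontinuations for events judged related to study drug.
- No minimum hold is stated. The investigator must already assess every ECG under 7.2.4.1, and under 3.6 the investigator's agreement is enough without the SRC.
- The ECG and the injection fall at the same visit. The windows are Day 29 ± 1 and Day 57 ± 1, so same-day clearance keeps the dose on schedule. Only a review that pushes dosing more than 1 day past the nominal day takes it outside the window.

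**Step 4. How many subjects?** The documents do not say. For scale only, let an assumed share p of the 36 subjects (3 × 12) have stable block. The expected number is 36p and the chance of at least one is 1 − (1 − p)^36.

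| Assumed p | Expected number | Chance of at least one |
|---|---|---|
| 2% | 0.7 | 0.52 |
| 5% | 1.8 | 0.84 |
| 10% | 3.6 | 0.98 |
| 15% | 5.4 | 0.997 |

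These shares are assumptions, not estimates for this population, and the conclusion does not rest on them.

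**The case against.** The strongest reply is that the rule does little harm and may even help. Read literally, it applies before dose 1, so a subject with pre-existing block is assessed before any exposure and the rule acts as an entry check. The investigator reviews every ECG with a baseline tracing to hand and can clear an unchanged one at the same visit. Earlier human exposure was to single doses in healthy subjects, so a cautious hold is defensible in a repeat-dose study in patients. The analyses are descriptive, and no endpoint or escalation decision is shown to change.

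Most of this stands, and it limits the size of the point. It does not remove it. The investigator's ECG assessment is not written as an exception to the mandatory hold. The return clause in 3.6 is a case-by-case remedy with no criteria, and clearing a subject once does not stop the trigger at the next dose. The case for caution supports keeping higher-degree block absolute and catching new bundle branch block. It does not support holding drug for an unchanged one.

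A reader might infer that an affected subject loses two of three doses, or the third-dose pharmacokinetic profile. The documents do not support either. A hold is not a lost dose. The third-dose samples are timed from the dose itself, so a delayed dose 3 still allows a full profile. Only an outright missed dose 3 in an active subject would forfeit it, and nothing in the plan makes that the expected result.

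**Conclusion.** The point holds as a mismatch between the entry rules and one hold rule. Followed as written, section 7.2.4.1 holds drug in an eligible subject whose bundle branch block has not changed, at two dosing visits or at all three depending on whether the pre-dose ECG counts.

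The consequence is small: an unneeded hold and review at each such visit, which the investigator may clear the same day, with a delayed or missed dose only possible. Pharmacokinetic loss is not quantified, because any figure would need a hold length or an outright missed dose that the documents do not supply.

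The focus on bundle branch block rather than higher-degree block is a clinical judgement: an investigator is more likely to use exclusion 23 for the latter. The absence of a named exclusion for second- or third-degree block might be read as a safety gap that must be closed. The documents do not support that, since exclusion 23 can already keep such subjects out and the hold would still apply to them.

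**What to change.** Reword the third bullet of 7.2.4.1 to: *second- or third-degree heart block, or new or worsened bundle branch block compared with the Day 1 pre-dose ECG*. Where footnote a of Appendix 6 lets a screening ECG taken within 3 days before Week 0 serve as baseline, that ECG is the reference. A short definition of worsened would help sites apply the rule consistently; averaged QRS values already go into the eCRF and could support one.

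An exclusion for pre-existing second- or third-degree block in section 4.2 and the synopsis is optional. It is an eligibility choice and is not needed for this fix.

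No new assessments or data are required. The change does need an amendment with ethics approval and, where locally required, regulatory approval, and the Chinese protocol has to stay aligned, so it is best carried with the next amendment. The clinical cost is that a fixed bundle branch block present at baseline no longer triggers an automatic hold, although the investigator still assesses every ECG.

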7.2.5. Physical Examination

A full physical examination or symptom-directed physical examination will be performed at the timepoints specified in the Schedule of Assessments in [Appendix 6](#). Full physical examination will usually only be performed at Screening or Day-1.

7.2.6. Body Weight

Body weight will be recorded at the timepoints indicated in the Schedule of Assessments in [Appendix 6](#).

7.2.7. Immunogenicity (ADA)

Blood samples for immunogenicity (anti-drug antibodies [ADA]) will be collected at the times indicated in the Schedule of Assessments in [Appendix 6](#).

Neutralization activity will be evaluated if ADA is positive.

7.2.8. Pregnancy test

Females of reproductive potential will be tested at the times indicated in the Schedule of Assessments in [Appendix 6](#).

7.3. Efficacy Assessments:

7.3.1. Right heart catheterization (RHC)

The data will be collected at the times indicated in the Schedule of Assessments in [Appendix 6](#).

7.3.2. Echocardiogram (ECHO)

Echocardiogram will be recorded at the times indicated in the Schedule of Assessments in [Appendix 6](#).

7.3.3. Six-minute walk test (6MWT)

The 6MWT will be collected at the times indicated in the Schedule of Assessments in [Appendix 6](#). The operation details of 6MWT is described in the Site Operation Menu. Borg index score will be collected immediately after 6MWTs.

7.3.4. NT-pro-BNP

The data will be collected at the times indicated in the Schedule of Assessments in [Appendix 6](#).

7.3.5. WHO functional class

The data will be collected at the times indicated in the Schedule of Assessments in [Appendix 6](#).

7.3.6. The REVEAL risk score

The data will be collected at the times indicated in the Schedule of Assessments in [Appendix 6](#).

8. SAMPLE SIZE AND DATA ANALYSIS

8.1. General Analysis

Statistical analyses will be descriptive only, with no hypothesis testing. Analyses will be performed in SAS®. Summary tables will present results for each of the three GMA301 doses. Descriptive statistics including the number (n), the arithmetic mean (Mean), standard deviation (SD), median, the minimum value (Min), and the maximum value (Max) will be presented for continuous variables, and the number of subjects (n) and the percentage (%) will be presented for categorical and ordinal variables. All study data will also be presented in by subject data listings. The details of the statistical analysis will be described in the Statistical Analysis Plan (SAP).

8.2. Determination of Sample Size

No formal statistical assessment, in terms of sample size, has been conducted. Approximately 36 subjects will be randomized into 3 treatment cohorts with GMA301-assigned subjects receiving either 300, 600, or 1000 mg injections of the study drug depending on their assigned cohort. Each cohort will include 12 subjects, 9 of whom will be administered active GMA301 and 3 of whom will receive placebo.

The number of subjects in each cohort of the present study is common in early clinical pharmacology studies and is considered sufficient to achieve the objectives of the study.

8.3. Analysis Populations

8.3.1. Pharmacokinetic Population

The PK population will include all subjects who received at least 1 dose of study drug (GMA301) and have at least 1 evaluable PK data.

8.3.2. Safety Population

The safety population will include all subjects who received at least 1 dose of study drug. The safety population will be analyzed according to treatment actually received.

Any subject who did not receive the treatment randomly assigned will be listed, but will be included in all analyses according to the treatment actually received.

8.4. Demographics and Other Baseline Characteristics

8.4.1. Baseline demographics

Demographic and baseline characteristics will be listed and summarized by treatment group and overall for the Safety Population. Characteristics will include but not limited to age, weight, height, body mass index, sex, and race. No formal statistical comparisons will be made between treatment groups.

8.4.2. Medical History

Medical History will be coded according to the current version of MedDRA. The Medical Histories will be listed and numbers and percentages of any medical history will be summarized for the safety population by system organ class and preferred term for each treatment group, and overall.

8.5. Pharmacokinetic Analyses

Non-compartmental PK analysis will be performed on individual serum concentration data, using commercial software such as Phoenix® WinNonlin®. Serum concentrations of GMA301 and PK parameters will be listed and summarized using descriptive statistics. Individual and mean GMA301 concentration-time profiles will also be presented graphically.

In the study, where data are available, GMA301 dose proportionality will be examined across dose groups. The PK parameters will be analyzed for dose proportionality using a power model approach or analysis of variance (ANOVA) model as appropriate.

Other parameters may be added as appropriate. Final PK parameters reported will be detailed in the SAP.

8.6. Safety Analysis

All safety analyses will be performed on the Safety Population. No formal statistical analysis of safety data is planned.

AEs will be coded by System Organ Class and Preferred Term using the current version of the MedDRA dictionary. Safety parameters will be listed and summarized using descriptive statistics. No formal statistical analysis of safety data is planned. Safety data will be summarized by dose group. Incidences of TEAEs (those events that started after exposure to study drug or worsened in severity after dosing) will be presented by dose group as well. Incidences of TEAEs will be presented by maximum severity and relationship to study medication.

Laboratory test results, ECG results, vital sign results and their changes from Baseline will be summarized by dose group using descriptive statistics. Shift tables (low, normal, high) comparing baseline results to the worst post baseline results will be presented by parameters and dose group for laboratory results. Shift tables (normal, abnormal not clinically significant, abnormal clinically significant) comparing baseline results to the worst post baseline results will be presented by parameters and dose group for ECG results. Other safety measurements like physical examinations will be presented in listings.

Prior and Concomitant Medications will be classified according to the WHO Drug Dictionary. All usage will be listed. The current version of the WHO Drug Dictionary will be used. The frequency of usage of each medication class will be summarized using the WHO Drug hierarchy. The percentage of subjects in each dose using each class of medication after baseline will be presented.

The number and percentage of positive ADA and the positive neutralizing antibody at each timepoint will be summarized descriptively.

8.7. Efficacy Analyses

The Safety Population will be used for efficacy analyses.

Efficacy endpoints including hemodynamic parameters, 6-minute walk distance, NT-proBNP levels, WHO functional class, and their change from baseline will be listed and summarized by treatment group using descriptive statistics as appropriate at each collection timepoint.

8.8. Exploratory Analyses

REVEAL 2.0 risk score and their change from baseline will be listed and summarized descriptively by treatment group at each collection timepoint.

8.9. Interim Analysis

Not applicable.

10. APPENDICES

Appendix 1: Adverse Event Reporting

Definitions

An AE is any untoward medical occurrence in a subject or clinical investigation subject administered a pharmaceutical product, which does not necessarily have a causal relationship with this treatment. An AE can therefore be any unfavorable and/or unintended sign (including a clinically significant abnormal laboratory finding), symptom, or disease temporally associated with the use of a study drug, whether or not related to the study drug.

Assessment of Severity

The Investigator will be asked to provide an assessment of the severity of the AE using the following categories:

- **Mild:** event is medically significant but produces no disruption to daily activity;
- **Moderate:** event is medically significant and reduces or affects normal daily activity;
- **Severe:** event is medically significant and results in inability to work or perform normal daily activity.

Relationship to Study drug

The Investigator will make a determination of the relationship of the AE to the study drug using a 4-category system according to the following guidelines:

- **Not Related:** The AE is definitely caused by the subject's clinical state or the study procedure/conditions.
- **Unlikely Related:** The temporal association between the AE and the drug is such that the drug is not likely to have any reasonable association with the AE.
- **Possibly Related:** The AE follows a reasonable temporal sequence from the time of drug administration but could have been produced by the subject's clinical state or the study procedures/conditions.
- **Related:** The AE follows a reasonable temporal sequence from administration of the drug, abates upon discontinuation of the drug, follows a known or hypothesized cause-effect relationship, and (if appropriate) reappears when the drug is reintroduced.

Follow-up of Adverse Events

Every reasonable effort will be made to follow up with subjects who have AEs. Any subject who has an ongoing AE that is possibly related or related to the IMP or study procedures at the Follow-up visit will be followed up, where possible, until resolution or until the unresolved AE is judged by the Investigator (or designee) to have stabilized. This will be completed at the Investigator's (or designee's) discretion. Any

subject who has an ongoing AE that is not related or unlikely related to the IMP or study procedures at the Follow-up visit can be closed out as ongoing at the Investigator's discretion.

Adverse Drug Reactions

All noxious and unintended responses to an IMP (ie, where a causal relationship between an IMP and an AE is at least a reasonable possibility) related to any dose should be considered adverse drug reactions.

For marketed medicinal products, a response to a drug which is noxious and unintended and which occurs at doses normally used in man for prophylaxis, diagnosis, or therapy of diseases or for modification of physiological function is to be considered an adverse drug reaction.

An unexpected adverse drug reaction is defined as an adverse reaction, the nature or severity of which is not consistent with the applicable product information (eg, Investigator's Brochure for an unapproved IMP).

Serious Adverse Events

A SAE is defined as any untoward medical occurrence that at any dose either:

- results in death
- is life-threatening
- requires in subject hospitalization or prolongation of existing hospitalization
- results in persistent or significant disability/incapacity (disability is defined as a substantial disruption of a person's ability to conduct normal life functions)
- results in a congenital anomaly/birth defect
- results in an important medical event (see below).

Important medical events that may not result in death, be life-threatening, or require hospitalization may be considered SAEs when, based upon appropriate medical judgment, they may jeopardize the subject and may require medical or surgical intervention to prevent one of the outcomes listed in this definition.

Instances of death or congenital abnormality, if brought to the attention of the Investigator at any time after cessation of the study drug and considered by the Investigator to be possibly related to the study drug, will be reported to the Sponsor.

Definition of Life-threatening

An AE is life-threatening if the subject was at immediate risk of death from the event as it occurred (ie, does not include a reaction that might have caused death if it had occurred in a more serious form). For instance, drug-induced hepatitis that resolved without evidence of hepatic failure would not be considered life-threatening even though drug-induced hepatitis can be fatal.

Definition of Hospitalization

AEs requiring hospitalization should be considered serious. In general, hospitalization signifies that the subject has been detained (usually involving an overnight stay) at the hospital or emergency ward for observation and/or treatment that would not have been appropriate at the Clinical Research Unit. When in doubt as to whether hospitalization occurred or was necessary, the AE should be considered as serious.

Hospitalization for elective surgery or routine clinical procedures, which are not the result of an AE, need not be considered AEs and should be recorded on a Clinical Assessment Form and added to the electronic Case Report Form. If anything untoward is reported during the procedure, this must be reported as an AE and either 'serious' or 'nonserious' attributed according to the usual criteria.

Serious Adverse Event Reporting

FDA-reportable SAEs are AEs that are associated with the use of the drug and are serious and unexpected. Food and Drug Administration-reportable AEs will be reported by the study site to the Sponsor, and the responsible Institutional Review Board (IRB).

The Sponsor and Medical Monitor will be notified in writing (eg, facsimile) within 24 hours when a SAE that is FDA-reportable is firstly recognized or reported.

Subsequently, a written confirmation or summary of the AE (using FDA Form 3500A or equivalent) will be sent to the Sponsor within 3 working days of the original notification.

The IRB will be notified of any FDA-reportable AEs within the timeframe required by the IRB. The IRB Serious and Unexpected Adverse Experience Submission Form will be completed and submitted with the copy of the written confirmation or summary of the AE.

The responsibility for reporting SAEs will be transferred to the Sponsor 30 days after the end of the study.

Pregnancy

Pregnancy (maternal or paternal exposure to study drug) does not meet the definition of an AE. However, to fulfill regulatory requirements any pregnancy should be reported following the SAE process to collect data on the outcome for both mother and fetus.

All the female subjects of child-bearing potential will be educated formally before they sign the ICF in order to be compliance with FDA's requirements.

